4. STUDY TREATMENT

4.1 EDTA Eye Drops

Livionex Inc. has agreed to supply EED. It consists of 2.6% EDTA plus a permeation enhancer (MSM). EED will be packaged in standard dropper bottles and labeled as containing 2.6% EDTA plus MSM as a surfactant.

4.2 Comparator: Abreva®

Abreva, manufactured by Avinir Pharmaceuticals, is an antiviral agent approved by the FDA for treatment of cold sores. It is packaged in tubes of 2g each.

4.3 Randomization Codes

A simple randomization code will be generated by the Investigator so that subjects are randomly assigned in a 1:1 ratio to either EED or Abreva.

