Design	
This will be a randomized, efficacy assessor-blinded, parallel group, pilot study of up to 20 subjects with documented MED induced herpes labialis.
 
Potential subjects will be assessed during a screening visit that must take place no greater than 2 weeks prior to the lesion induction visit. During the screening period, subjects that meet all other entry criteria will undergo UV susceptibility testing to determine their individual MED (minimal erythema dose). UV susceptibility testing takes place over two days with exposure to UV light on specified regions on the subject's back followed by an assessment of the exposed areas 24 hours later to identify the MED. Subjects who have a measurable MED will be allowed to continue to the induction visit. Patients that do not have a measurable MED response will be considered screen failures or they may have repeat MED testing with different levels.
 
At the Induction Visit, subjects will undergo UV radiation at a level 3 times their MED. The exposed area of the lip will be marked with indelible ink and a photograph may be taken. Each subject will then be randomly assigned in a 1:1 ratio to receive either EED or Comparator. Subjects will be dispensed

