3. STUDY DESIGN

This will be a randomized, efficacy assessor-blinded, parallel group, pilot study of up to 20 subjects with documented UV induced herpes labialis. We will enroll until we have 20 subjects that have expressed a lesion from the induction and complete the treatment period of the study. With the possibility of screen failures and induction failures, we may consent up to 35 patients maximum.

Potential subjects will be assessed during a screening visit that must take place no greater than 2 weeks prior to the Induction visit. During the screening period, subjects that meet all other entry criteria will undergo UV susceptibility testing to determine their individual MED (minimal erythema dose). UV susceptibility testing takes place over two days with exposure to UV light on specified regions on the subject's back followed by an assessment of the exposed areas 24 hours later to identify the MED.

Subjects who have a measurable MED will be allowed to enroll in the study. Each subject will be randomly assigned in a 1:1 ratio to receive either EED or Comparator.

Subjects that do not have a measurable MED will be considered screen failures or may have repeat MED testing with new values.

At the Induction Visit, subjects will undergo UV radiation at a level 3 times their MED. The exposed area of the lip will be marked with indelible ink and a baseline photograph may be taken.

Each subject will then be randomly assigned in a 1:1 ratio to receive either EED or Comparator. Subjects will be dispensed study medication and instructed how to apply it to the exposed area. Dosing of the study product will be done 5 times daily, beginning at the time that a subject first senses the start of the prodromal phase (Day 1). The EED is a clear viscous eye drop, and the Comparator is a white cream substance. Therefore, the subject and principal investigator will be unblinded, and only efficacy assessments will be done by a qualified trained blinded assessor.

Subjects will be given a diary card to record their pain levels (starting at Day 1), progression of lesion development and any unusual symptoms (not normally seen with their outbreaks).

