6. STUDY PROCEDURES

6.1 Study Visits

6.1.1 Screening Visit (Days -14 to 0)

No more than 14 days prior to their planned start of study, subjects will report to the dermatology clinic for the following screening procedures:

- Presentation, review and signing of the informed consent.
- Review of their medical history.
- Review of HSV history.
- Assist with setting up MyChart account.
- Review of Inclusion and Exclusion criteria.
- Limited Physical Exam – to ensure that there are no co-morbidities that may interfere with study compliance or results.
- Notation of any concomitant medications the subject is currently taking (and that do not conflict with entry criteria).

ONLY IF the subject meets all entry criteria and is considered by the Investigator to be able to comply with and complete all study procedures, may they proceed to the final screening procedure of UV Susceptibility and Calculation of MED (refer to Study Manual for detailed instructions) consisting of:

- Exposure to UV Radiation.
- Assessment of Exposed Area – no more than 24 hours after exposure.

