6.1.2 Induction Visit

Upon reporting to the clinic for their induction visit, the subject will be randomized to receive either EED or Abreva. The following assessments will then be performed to establish baseline values prior to dosing:

- Review of Medical History and Concomitant Medications for any changes between Screening and Day 1 (Treatment emergent AEs are collected in this study beginning with first instance of dosing. Any unusual symptoms prior to the start of dosing will be recorded, if appropriate, as an update to the subject's medical history).

- Limited Physical Exam to check for any changes between Screening and Day 1(changes in PE after start of dosing will be assessed as possible treatment emergent AEs)

If the subject remains qualified for the study:

- They will be dispensed study product (EED or Abreva) and instructed to use it 5 times daily beginning when they first sense a prodrome or see a lesion (they will be asked to note the day and time of their first dose on their diary card).
- They will be given a diary card and instructed how to complete it. A practice diary completion may be done to ensure that subjects know how to complete the diary.

Subjects will then be discharged from the clinic with an appointment to return on Day 3 via virtual video call. They will be instructed to bring their Diary Card and the tube/bottle of study product that they have received.

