9. STATISTICAL METHODS

9.1 Analysis Populations

Analysis populations are defined as follows:

- The Safety population will include all subjects who use EED or Abreva for at least one day.
- The Per Protocol population will include all subjects (that were not induction failures) who complete the study, defined as attending all study visits.

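### The unblinded Investigator who judges entry also generates the randomisation code with no concealment described, and Section 6.1.2 as written allocates before a residual eligibility re-check

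*Combined protocol and SAP*

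**What the plan says.** **Code and entry.** Section 4.3 is the only text on generating the code: "A simple randomization code will be generated by the Investigator", with 1:1 allocation. It does not say who holds the code or how an assignment is released. Under Section 6.1.1 a subject goes on to MED testing only if the entry criteria are met and the subject "is considered by the Investigator to be able to comply with and complete all study procedures". Section 3 explains that the two products look different, so the subject and the principal investigator are unblinded and only the efficacy rating is blinded.

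**Order at the Induction Visit.** Section 6.1.2 begins: "Upon reporting to the clinic for their induction visit, the subject will be randomized to receive either EED or Abreva". It continues: "The following assessments will then be performed to establish baseline values prior to dosing". These assessments look for changes since screening in history, medications and physical findings. Product and diary are handed out afterwards, under the condition "If the subject remains qualified for the study". The synopsis (Design) and Section 3 instead describe irradiation, marking of the lip and an optional photograph, followed by: "Each subject will then be randomly assigned in a 1:1 ratio to receive either EED or Comparator". Section 3 also has an earlier sentence with no time attached: "Each subject will be randomly assigned in a 1:1 ratio to receive either EED or Comparator".

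**Who is analysed.** Section 9.1 defines two populations. For the first: "The Safety population will include all subjects who use EED or Abreva for at least one day". The second, Per Protocol, requires attendance at every visit and excludes induction failures. Section 5 continues enrolment until 20 subjects have had a lesion and finished treatment, with at most 35 consented.

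**The concern.** A randomised comparison is protected at entry only if the person deciding on entry cannot know the next assignment. The entry criterion in Section 6.1.1 includes a judgement about likely compliance, and such a judgement can be swayed. Blinding the efficacy assessor does not help here, because it acts after allocation. With the principal investigator unblinded, concealment up to the moment of assignment is the safeguard that remains at entry, and the plan does not describe it.

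The order in Section 6.1.2 adds a second opening. If the arm is already assigned when someone decides whether the subject still qualifies, that decision can also depend on the arm. Enrolment would simply continue to 20 completers, and the missing subject would appear in no planned analysis.

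**Working it through.** The plan gives no figure on this point and no arithmetic applies, so the check compares the texts.

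**Step 1: is concealment described anywhere?** Section 4.3 names who generates the code and the ratio, and nothing else. Section 6.1.1 refers to a Study Manual, but only for UV susceptibility and MED. Section 8.1.4 speaks of breaking the blind but names no code holder. There is no mention of envelopes, central or pharmacy release, or an independent code holder.

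**Step 2: when does randomisation happen?** There are five statements.

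| Place | Randomisation relative to UV exposure | Randomisation relative to the re-check |
|---|---|---|
| Synopsis, Design | After | Re-check not mentioned |
| Section 3, first sentence | No time given | Re-check not mentioned |
| Section 3, second sentence | After | Re-check not mentioned |
| Section 6.1.2 | UV not mentioned; randomised on arrival | Before |
| Section 10 table | Same visit; the UV row is below randomisation | Same visit; the check rows are above randomisation |

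**Step 3: does one order satisfy all of them?**

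- Randomise, re-check, dispense, with UV at some point after arrival: this follows Section 6.1.2 but not the synopsis or the second sentence in Section 3.
- UV, randomise, re-check, dispense: this fits the synopsis, Section 3 and most of Section 6.1.2, except randomisation on arrival. The re-check still follows allocation.
- Checks, randomise, UV, dispense: this is the row order in Section 10. It departs from Section 6.1.2 on the re-check, and from the synopsis and Section 3 on UV.

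No order satisfies every statement. Section 6.1.2 is the only prose that places the re-check, and it places it after allocation wherever UV falls.

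**Step 4: what happens to a subject disqualified at the re-check?** Product has not been dispensed, so the subject cannot have a day of use (Safety, Section 9.1) or a single use (the safety wording in Section 8.1.2). The subject will not attend all visits (Per Protocol) and is not one of the 20 completers (Section 5). No all-randomised population is defined.

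**The case against.** The best defence is that the opening is narrow. The entry criteria and the Investigator's judgement come before MED testing, and a measurable MED is needed to continue. The later checks cover at most the 14 days since screening and are described as setting baseline values. Section 6.1.2 does not say who decides that a subject no longer qualifies. A simple code also cannot be predicted from past assignments. All of this stands and limits the likely size. It does not remove the problem: unpredictability gives no protection against someone who made the list, and the condition before dispensing is an eligibility decision placed after allocation.

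Four stronger readings are tempting but are not supported:

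- *Allocation is unconcealed.* The documents show only that concealment is not described. Whoever generates the code need not hold it or see the next assignment.
- *Section 6.1.2 flatly contradicts the synopsis and Section 3 on UV exposure.* It does not mention UV; its position relative to UV is inferred from randomisation on arrival. The silence of the synopsis and Section 3 about a re-check is not disagreement either.
- *Nothing in the plan puts the checks before randomisation.* The Section 10 rows list history, physical examination, medications and MED reading above randomisation. Row order is not an explicit time rule, but it points that way and should be acknowledged.
- *The gap of 35 − 20 = 15 subjects measures the loss.* That allowance is for screen failures and induction failures. Screen failures precede randomisation, and induction failures are a different loss after it. It says nothing about disqualification at the re-check.

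**Conclusion.** The point holds as a change that should be made. Two stated rules, the Investigator generating the code and Section 6.1.2 allocating before the re-check, leave room for selection at entry and for exclusions after allocation that no analysis would reveal. The order within the Induction Visit is also not consistent across the protocol.

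The size cannot be computed. The documents do not say how often the next assignment could be known or how many subjects might be disqualified at the re-check, and that number may be zero. The conclusion takes the Investigator of Sections 4.3 and 6.1.1 to be the unblinded principal investigator of Section 3; the front page lists a single investigator.

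Confidence is high on what the text says about code generation and the order in Section 6.1.2, and moderate on where randomisation falls relative to UV exposure. The pilot label does not dispose of the point, because Section 9.2 tests the primary endpoint between randomised groups.

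**What to change.** 1. In Section 6.1.2, place randomisation after the eligibility re-check and, as the synopsis and Section 3 already have it, after UV exposure, immediately before dispensing. Use this one order in the synopsis and Sections 3, 6.1.2 and 10. Remove the earlier untimed randomisation sentence in Section 3, or give it a time. The statistical requirement is only that both the re-check and UV exposure precede randomisation; their order relative to each other is for the protocol team to state.
2. In Section 4.3, have the code generated and held by existing staff with no role in enrolment or assessment. Release each assignment only after eligibility is confirmed, for example by sequentially numbered opaque sealed envelopes. This assumes that such a person exists at the site; the documents name none.

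The cost is protocol wording, one list produced once, and minor logistics at dispensing. The change does not address induction failures, which arise after randomisation, or the lack of an all-randomised population in Section 9.1.

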Patients will be called daily by the study team after their induction visit to determine the start of prodrome. When the patient first senses the prodromal phase, they need to be seen within 24 hours for the Day 1 visit. Patients that do not have prodromal senses within 7 days of the induction will be considered induction failures. Induction failure patients will be asked to return their study drug to the study team.

On Days 1, 3, 5, and 7 the subject will follow up in person or via virtual MyChart visit with blinded assessor during which the subject's diary card will be reviewed and compliance with dosing checked. If the subject has noted any unusual symptoms, these will be discussed with medical personnel to determine if a treatment emergent adverse event has occurred or, if the subject has not started treatment, whether their medical history should be updated. If possible, the lesion will be measured. A photo will be taken of the irradiated area (as marked at the induction visit). More study drug may be dispensed as needed. Most subjects' lesions will have resolved by day 7, and they will end study treatment after 7 full days of

treatment. If lesion has not resolved by day 7, the maximum number of days the patient may use study drug treatment is 10 days. An end of study (EOS) visit will occur as soon as their lesion is healed or Day 10, whichever comes first.

The EOS visit (Day 10) is expected to be the final study visit. EOS will occur when a subject's lesion is fully healed or Day 10 (whichever comes first). A photo will be taken of the irradiated area, the diary card will be carefully reviewed and study product (including empty containers) will be collected. Subjects who developed a lesion that has not yet healed will be given the option to begin taking a prn medication that has been previously prescribed to treat an outbreak.

If an adverse event has occurred but has not resolved by the EOS visit, the subject will be contacted once weekly, and status of the AE noted until such time as the event has resolved.

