5. SUBJECT POPULATION

We will enroll until we have 20 subjects that have expressed a lesion from the induction and complete the treatment period of the study. With the possibility of screen failures and induction failures, we may consent up to 35 patients maximum.

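### Section 4.3's simple randomisation gives 1:1 only on average; permuted blocks of varying size would make a lopsided split among 20 evaluable subjects much less likely at almost no cost

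*Combined protocol and SAP*

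**What the plan says.** Section 4.3 is the only description of the method: "A simple randomization code will be generated by the Investigator so that subjects are randomly assigned in a 1:1 ratio". Section 3 repeats the ratio: "Each subject will then be randomly assigned in a 1:1 ratio to receive either EED or Comparator". Blocking, stratification and minimisation are not mentioned anywhere.

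Section 5 sets the number: "We will enroll until we have 20 subjects that have expressed a lesion from the induction and complete the treatment period of the study". It adds: "With the possibility of screen failures and induction failures, we may consent up to 35 patients maximum".

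On timing, section 6.1.2 states: "Upon reporting to the clinic for their induction visit, the subject will be randomized to receive either EED or Abreva". Section 3 defines the later loss: "Patients that do not have prodromal senses within 7 days of the induction will be considered induction failures". Section 9.1 removes those subjects from the efficacy-relevant set: "The Per Protocol population will include all subjects (that were not induction failures) who complete the study, defined as attending all study visits".

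Section 3 also makes clear that the subject and the principal investigator know the treatment, because the two products look different.

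**The concern.** In statistical usage, simple randomisation means an independent 50:50 draw for each subject. In a large trial the arms come out nearly equal. With 20 subjects, sizeable imbalance is common, and nothing in the plan limits it.

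An unequal split makes every between-group comparison in section 9.2 less precise than the same 20 subjects could give: the primary proportion, the t-tests on duration and lesion size, and the healing-time curves. The trial is already very small and may recruit for two years, so a poor split could not easily be repaired. At stake is some precision that a different list would mostly keep.

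**Working it through.** **Inputs.** Evaluable target 20 (section 5). Assignment probability 0.5 (sections 3 and 4.3). At most 35 consented (section 5), which caps the number randomised. The documents give no induction-failure rate, so 20 to 35 randomised is taken as the range. They give no power, alpha or effect size for the 20 and no probability of imbalance, so there is no planned figure to reproduce.

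**Step 1: chance of imbalance under simple randomisation.** Let X be the number of evaluable subjects on EED. If induction failure and completion do not depend on arm, X is Binomial(20, 0.5), however many were randomised. For induction failure this is plausible, since dosing starts only at the prodrome. Both directions are counted:

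P(split k:(20−k) or worse) = 2 × Σ C(20, x) / 2^20, for x = 0 to k.

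For k = 7: 2 × 137,980 / 1,048,576 = 0.263. Exactly 10:10: 184,756 / 1,048,576 = 0.176.

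**Step 2: cost in precision.** With equal variance per subject in the two arms, the variance of the difference relative to 10:10 is (1/n1 + 1/n2) / (1/10 + 1/10).

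| Split | Chance of this or worse | Relative variance | Efficiency kept |
|---|---|---|---|
| 7:13 | 26.3% | (1/7 + 1/13)/0.2 = 1.10 | 91% |
| 6:14 | 11.5% | (1/6 + 1/14)/0.2 = 1.19 | 84% |
| 5:15 | 4.1% | (1/5 + 1/15)/0.2 = 1.33 | 75% |

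Averaged over all splits that simple randomisation can produce, the variance is about 6% higher than at 10:10.

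**Step 3: cost in power, for scale only.** The plan states neither response rates nor alpha. Assuming two-sided 5%, approximate power at 10:10 and at 7:13 is:
- 60% v 30%: 26.1%, falling to 23.5–25.1%
- 70% v 30%: 42.6%, falling to 39.7%
- 80% v 30%: 63.0%, falling to 58.3–60.6%
- 90% v 30%: 83.8%, falling to 79.6–81.9%

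The ranges depend on which arm is smaller. The loss is about 1 to 5 percentage points.

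**Step 4: what blocking would leave.** Blocks balance the subjects randomised, not the 20 analysed. Permuted blocks of 4 and of 6 were simulated (100,000 runs each), taking 20 evaluable subjects at random from those randomised:

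| Randomised | Chance of 7:13 or worse, blocked |
|---|---|
| 20 to 22 | 0% |
| 25 | about 1.5% |
| 28 | about 3–5% |
| 30 | about 5–6% |
| 35 | about 9% |

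Drawing each block size at random from 4 and 6 gave much the same results in a further simulation (60,000 runs, the last subject randomised always evaluable): about 6% at 30 and 10% at 35. The comparison figure is 26.3% in every row. Because screen failures also count towards the 35 consented, the last row is the extreme case.

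**The case against.** The strongest reply is that this is a design preference. Simple randomisation is a valid 1:1 allocation, and no section promises 10 subjects per arm. It is also the least predictable method, which has value when the subject and investigator know the treatment and the Investigator generates the code. The study is a pilot with no power target to miss, and a 7:13 split keeps 91% of the efficiency. The section 4.3 wording may also be everyday language for an uncomplicated list. All of this stands. It limits the size of the point but does not remove it: if the wording is loose, the method is simply unstated and the sentence still needs revising.

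Four stronger readings that a reader might infer are not supported:
- *The stated ratio is not delivered.* It is delivered in expectation. The most that can be said is that equal arms are not guaranteed.
- *Precision is lost for no reason.* The reason is unpredictability, a real advantage to be weighed against the loss.
- *One arm would be too small to describe.* Even five subjects can be described, and 5:15 or worse has a 4.1% chance.
- *Imbalance is where the chi-square test exceeds its level.* The documents state no alpha. At an assumed two-sided 5% without continuity correction, the maximum exact size is 4.2% at 10:10, 5.7% at 9:11, 5.9% at 8:12 and 7:13, 4.0% at 6:14 and 5.2% at 5:15. The excess is small and does not track imbalance, and blocking would not rule out 9:11 or 8:12 among evaluable subjects.

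**Conclusion.** The point holds as a cheap improvement. As written, section 4.3 leaves about a one-in-four chance of 7:13 or worse among the 20 evaluable subjects and about a one-in-nine chance of 6:14 or worse. Blocking would remove most of that risk, though not all of it once randomised subjects drop out as induction failures. How much remains depends on a failure rate that the documents do not give.

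The conclusion rests on three assumptions: the wording means unrestricted randomisation; loss from the evaluable set is unrelated to arm; and between 20 and 35 subjects are randomised. The second would weaken if a product changed who completes, or if the requirement in section 5 to have expressed a lesion were applied so strictly that a treatment effect altered who counts. The stakes are modest precision. A trial run under the present code would still be a valid randomised comparison.

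**What to change.** Rewrite section 4.3 to name the method: 1:1 permuted blocks, with each block's size drawn at random from a small set of even numbers (for example 4 and 6). State that the list is generated and held by someone other than the Investigator and the enrolling staff, that block sizes are not disclosed to them, and that each assignment is released only once the subject is confirmed eligible at the induction visit. Add a sentence acknowledging that blocking balances the subjects randomised and that the evaluable arms may still differ in size.

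The cost is a different list and a person to hold it. The downside is that the last assignment in a block may be guessable where treatment is known after dispensing; varying sizes and concealment limit this. Holding the list away from the Investigator is worthwhile even if the simple code is kept.
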